Bacterial Wound Contamination Prior to Closure: Povidone-iodine versus Saline Irrigation in Pediatric Spine Fusion Surgery

Version Date: October 16, 2017

Principal Investigator:

*[name]
Assistant Professor, Harvard Medical School
Department of Orthopaedic Surgery
Children's Hospital Boston
[name]
[name]
[contact]*

Co-Investigator:

*[name], MD
Richard M. Armstrong Jr. Professor of Orthopaedic Surgery
Perelman School of Medicine at the University of Pennsylvania
Chief of Orthopaedic Surgery
The Children's Hospital of Philadelphia
[name]
[name]
[contact]*

Co-Investigator:

*[name]
Director, Orthopaedic Research Program
Chair, American Academy of Pediatrics, Section on Orthopaedics
[name] Surgery, University of Missouri-
Kansas City School of Medicine and University of Kansas Medical
Center
Children's Mercy Hospital & Clinics
[name]
[name]
[name]
[contact]*

A. Scientific Aims

The overall goal is to evaluate the safety and efficacy of surgical site irrigation with povidone-iodine in children and young adults undergoing spinal deformity surgery. More specifically, we will: (1) Establish safety of use of dilute povidone-iodine irrigation, (2) Establish baseline tissue colonization prior to closure, (3) Establish bacteriology of tissue contamination prior to closure, (4) Establish population (ie idiopathic vs neuromuscular) specific differences in tissue colonization prior to closure, and (5) Establish estimates for the effect that povidone-iodine/saline have on reducing bacterial contamination.

B. Significance

Due to their profound financial, personal, and societal costs, interventions focusing on preventing post-operative spine infection are of considerable interest.[1-5] The proposed study will hopefully demonstrate that using povidone-iodine irrigation in pediatric spinal patients is safe and reduces bacterial contamination of the spinal surgical wound prior to closure. Following this pilot and assuming there is a reduction in bacterial contamination, we would conduct a multicenter randomized controlled trial (RCT) to assess whether the reduction leads to a lower postoperative spinal infection rate.

C. Background

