Demographics, medications, medical history, and laboratory results will be collected from medical records. Surgical data will be collected during the fusion operation and two standard cultures of the surgical site will be taken during the surgery using the routine surgical pathology protocol at each institution. Results from the cultures taken at the fusion operation, in addition to any other associated post-operative cultures, will also be collected post-operatively from medical records.

D.6. Adverse Events and Reporting Procedures

The only foreseeable, but highly unlikely adverse event associated with participation in this trial is an increased level of iodine in the blood as a result of washing the wound site with povidone-iodine. Extra iodine in the body is excreted through urine. A healthy body without thyroid or renal abnormalities is able to excrete excess iodine without any problems.

The monitoring of adverse events will be conducted on an ongoing basis for the duration of the study. If an adverse event occurs, it will be reported immediately to the IRB and the investigators will re-assess the risk/benefit ratio of the study and submit any modifications deemed necessary to the IRB for approval.

D.7. Statistical Considerations

We project an accrual of 150 patients, resulting in 75 per treatment group. Patients will be recruited from “low risk” and “high risk” patient populations in a 3:1 fashion, respectively. “Low risk” patients are defined as those with an idiopathic condition and the “high risk” group will encompass all others. Within each patient “risk” group, randomization will be split evenly between saline and betadine in a 1:1 fashion. Positive cultures before and after irrigation will be monitored to establish the efficacy of povidone-iodine irrigation. 150 patients will provide good statistical precision for estimating the probability of a positive pre-irrigation culture, as shown in the following table. The table shows exact 95% confidence intervals (CI) for the estimated percentage over a plausible range of observed outcomes.

Observed percentage:	30/150=20%	37/150=24.7%	45/150=30%
95% CI:	(14%, 27%)	(18%, 32%)	(23%, 38%)

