It will be of interest to examine how the tissue colonization rate varies across subgroups such as neuromuscular and idiopathic patients, which we anticipate to accrue in approximately a 3:7 ratio. Under this assumption, and assuming an overall pre-irrigation colonization rate of 25% and a two-sided $\alpha=.05$ test there will be 69%, 90% and 98% power, respectively, to detect relative risks (RR) of 2.0, 2.5, and 3.0, respectively.

Finally, we expect that the probability of a positive post-irrigation culture in the control group will be about .12, with a further reduction to perhaps .05 in the povidone-iodine group. These results would correspond to a relative risk (RR) of .417. Because positive post-irrigation cultures are projected to be fairly rare events, the size of this pilot study will not provide high statistical power unless the true treatment effect is quite large. However, the study should provide useful preliminary information about the size of the treatment effect. For example, the following table shows the probability that the estimated positive culture rate in the povidone-iodine group that will be at least 4, 5.33, 6.67 or 8 percentage points lower than in the control group, assuming the true control rate is .12 and the true rate in the povidone-iodine group is .05, .04 or .03 (corresponding to RR's of .417, .33 and

.25, respectively. Calculations are based on exact binomial probabilities. Also shown is the power of the study under each set of assumptions, assuming a two-sided $\alpha=.05$ chi-square test.

Number of fewer pos. cultures (of 75) in treatment group.	Observed percentage point reduction	True rates RR		True rates RR		True rates RR	
		.12 vs .05	.417	.12 vs .04	.33	.12 vs .03	.25
≥ 3	$\geq 4\%$ reduction	79%		86%		91%	
≥ 4	$\geq 5.33\%$ reduction	70%		78%		85%	
≥ 5	$\geq 6.67\%$ reduction	58%		67%		76%	
≥ 6	$\geq 8\%$ reduction	47%		54%		65%	
	Power:	33%		43%		55%	

For example (see bolded entry), if the true rates of post-irrigation positive cultures are .12 and .05 in the control and povidone-iodine groups, respectively, corresponding to $RR=.417$, there is a 79% chance that the observed rates will differ by 4 percentage points or more (i.e., 3 or fewer positive cultures out of 75 in the treatment group compared with the number of positive cultures out of 75 in the control group). However, there is only a 33% chance of finding a statistically significant difference (power=33%).

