The principal investigator will conduct an evaluation of the progress of the research study on a quarterly basis including assessments of data quality and timeliness; participant recruitment, accrual, and retention; and a review of outcome and complication data to determine whether there is any change to the anticipated benefit-to-risk ratio of study participation and whether the study should continue as originally designed, should be changed, or should be terminated. A summary of these reports will be submitted to sites IRBs and to BCH as part of the annual renewal.

G. Data Safety Monitoring Plan

To ensure safety, an independent safety monitor will be appointed to assist with interim data review. The monitor and the study statistician will be completely unblinded to treatment-group-specific results. There will be one scheduled interim analysis, conducted when data from approximately 1/3 and 2/3 of the accrual goal become available. Interim analysis will focus on the comparison of the treatment groups with respect to the primary endpoint, positive culture rate before and after irrigation, using two-sample t-tests. A "stopping rule" using a truncated O'Brien-Fleming procedure will be used to guide the need for further discussion of the possibility of early stopping among a wider group, including the study investigators. (This rule will not be interpreted strictly but rather will be used as a guideline to trigger the need for a wider discussion.) Specifically, the rule is that the stopping boundary is met if the nominal p-value is $p<.001$ at the first look or $p<.0141$ at the 2nd look. The actual O'Brien-Fleming rule would use a nominal p-value boundary of $p<.00052$ at the first look but this is extremely conservative (i.e., it would take an extreme treatment effect to meet this criterion) so the boundary had been truncated to $p<.001$. Along with a criterion of $p<.0451$ at the final analysis, this algorithm ensures an overall type I error of $\alpha=.05$. The stopping rule has a minimal effect on statistical power, less than one percentage point.

In addition to the scheduled interim analysis, the safety monitor will review cases of positive culture results and adverse events. The safety monitor will also review any cases where a patient may require additional testing to follow up on a thyroid or

renal abnormality that develops and advise on whether a wider discussion of early stopping should take place. Such cases will also be reported to the IRB.

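### Section G's boundary on the culture comparison could stop an estimation pilot at about 100 patients on an exaggerated effect, and its power cost is understated on exact binomial counts

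*Combined protocol and SAP*

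**What the plan says.** **What the pilot is for.** Section A lists safety as Aim 1. Aims 2 to 4 cover baseline colonisation, bacteriology and population differences, and Aim 5 is to "Establish estimates for the effect that povidone-iodine/saline have on reducing bacterial contamination". Section B describes a later multicentre trial, with infection as its outcome, if contamination is reduced.

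**How the size is justified.** Section D.7: "We project an accrual of 150 patients, resulting in 75 per treatment group". It argues that "150 patients will provide good statistical precision for estimating the probability of a positive pre-irrigation culture" and tabulates exact confidence intervals. For the treatment comparison it expects that "the probability of a positive post-irrigation culture in the control group will be about .12, with a further reduction to perhaps .05". It concedes that power is low (33%, 43% and 55% for the three rate pairs it considers) but says "the study should provide useful preliminary information about the size of the treatment effect".

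**What Section G adds.** The section opens with safety as its purpose. It then sets a truncated O'Brien-Fleming boundary on the between-arm culture comparison at about 1/3 and 2/3 of accrual: p<.001, then p<.0141, with p<.0451 at the end. Crossing is used "to guide the need for further discussion of the possibility of early stopping among a wider group, including the study investigators", and the section adds that the rule is a guideline and not to be applied strictly. On cost it says: "The stopping rule has a minimal effect on statistical power, less than one percentage point".

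**The concern.** A boundary on a between-arm efficacy endpoint answers the question of whether there is enough evidence of a difference to stop. Aims 2 to 5 ask a different one: how large are the rates, and how large is the effect? If the trial stops because the interim difference was extreme, the estimate it hands to the next trial has been selected for being extreme. The baseline and subgroup estimates also rest on fewer patients than planned. The plan does not say how those aims would be met at 50 or 100 patients, or how an effect estimated after an early stop would be reported.

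At stake are the planning values for the multicentre trial. An exaggerated effect would lead to a next trial that is too small. The interim testing also has a price even if the boundary is never crossed, because the final criterion is lowered to .0451. Whether that price is as small as Section G says can be checked.

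**Working it through.** **Inputs.** From D.7: 75 per arm, control rate .12, povidone-iodine rate .05, .04 or .03, two-sided .05 chi-square. From Section G: looks at 1/3 and 2/3 of accrual, taken as 25 and 50 per arm, with nominal p of .001, .0141 and .0451 (|z| above 3.291, 2.455 and 2.004).

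**1. The plan's own power.** With p̄ the mean of the two rates and d their difference, power = Φ{[d − 1.96√(2p̄(1−p̄)/75)] / √[(.12×.88 + pT(1−pT))/75]}. For .12 vs .05: p̄ = .085, numerator .07 − 1.96×.04554 = −.0193, denominator .0452, ratio −.426, power 33.5%. The other pairs give 43.8% and 55.3%. The stated 33%, 43% and 55% are reproduced, so they rest on a normal approximation.

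**2. What it takes to cross at look 2.** z = (difference)/√(2p̄(1−p̄)/50).
- 5 vs 0 positives: .10/.0436 = 2.29, not crossed.
- 6 vs 0: .12/.0475 = 2.53, crossed.
- With 1, 2 or 3 positives in the povidone-iodine arm, the control arm needs at least 9, 10 or 12.

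The smallest favourable difference that crosses is therefore 6/50 = 12 points. That is more than any of the true differences D.7 considers (7, 8 and 9), so an estimate taken at a crossing must be too large.

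**3. Exact enumeration of the three-look design.** Binomial counts in steps of 25 per arm. Chi-square and the two-sample t-test named in Section G give the same results.

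| True rates | Crossed at look 1 | Crossed at look 2 | Mean reduction at look-2 crossing (points) | True (points) | Ratio | No positives on povidone-iodine at crossing |
|---|---|---|---|---|---|---|
| .12 vs .05 | 0.05% | 9.3% | 16.5 | 7 | 2.4 | 47% |
| .12 vs .04 | 0.07% | 13.3% | 16.3 | 8 | 2.0 | 55% |
| .12 vs .03 | 0.08% | 18.9% | 16.1 | 9 | 1.8 | 65% |

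Nearly all crossings come at about 100 patients. Where the povidone-iodine arm has no positives, the estimated relative risk is 0, which is no use for planning.

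**4. How much of this is due to stopping.** At .12 vs .05, the trials that cross at look 2 would average 13.4 points if carried to 150 (13.4/7 = 1.9 times). Over all trials, with every crossing acted on, the mean estimate is 7.3, 8.4 and 9.5 points against 7, 8 and 9.

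**5. Baseline precision.** Exact 95% interval for 37/150: 18% to 32%, as D.7 states. For 25/100: 17% to 35%. The width goes from 14.4 to 17.8 points.

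**6. Power cost of the rule.** One look at .05 against the three-look rule, both with exact binomial counts:
- .12 vs .05: 34.64 − 33.09 = 1.55 points
- .12 vs .04: 45.96 − 43.56 = 2.40 points
- .12 vs .03: 58.94 − 55.85 = 3.09 points

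On a continuous normal process the losses are 0.6, 0.7 and 0.8 points.

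**The case against.** **The rule does not end the trial.** A reader might infer that crossing stops accrual at about 100. Section G does not support that: crossing prompts a discussion. This stands, and it limits the point to what could follow. It does not remove the point, because the discussion includes the investigators and nothing in the plan says accrual would continue.

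**The exaggeration is not always twofold, and stopping is not its only cause.** A reader might infer that the estimate is more than doubled in general, or that the pilot's estimate is biased overall. Neither holds. The ratio is 1.8 at .12 vs .03. Crossing is the minority outcome, the same trials carried to 150 would still run 1.9 times too high at .12 vs .05, and the average over all trials is nearly unbiased. Continuing lowers the excess (2.4 to 1.9 times) and keeps the other aims at full size. It does not remove the excess.

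**The comparison has legitimate uses.** The overall goal in Section A includes efficacy, and the boundary states no direction, so it also watches for more contamination with povidone-iodine. Deleting it outright would lose that, so the harm side should stay.

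**Stopping might benefit patients.** One might infer from D.3.b that saline patients get povidone-iodine anyway, so that stopping would spare nobody. The text leaves this to the surgeon's judgement, and some may not receive it. That argument is not relied on here.

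**The power statement is right on its own basis.** It is, under the normal approximation behind D.7's power figures. The trial will observe small binomial counts, and on those the loss exceeds one point at all three rate pairs. The statement is a matter of basis, not an arithmetical slip.

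**Conclusion.** The point holds as a mismatch between purpose and rule that is worth correcting. It is not a flaw that invalidates the pilot. Stopping on a favourable culture difference serves none of the estimation aims. If it happened, it would almost always be at about 100 patients, with a chance of about 9% to 19% of the boundary being crossed there. The reduction reported would average about 16 points against true values of 7 to 9. The loss of baseline precision is modest. The power cost is about 1.6 to 3.1 points on exact counts, against 0.6 to 0.8 under the approximation.

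These figures assume that the interim comparison is of post-irrigation cultures, that looks fall at exactly 25 and 50 per arm, that there is no dropout, and that D.7's rates are true. The mean reductions at crossing also assume that the crossing is acted on. Section G speaks of one interim analysis but gives two times and two boundaries. It is read here as two looks, and the wording should be reconciled.

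**What to change.** In Section G, state that a culture difference favouring povidone-iodine will not prompt early stopping and that accrual continues to 150. Keep the monitor's unblinded reviews at 1/3 and 2/3 of accrual for adverse events and for higher contamination with povidone-iodine. Test the final comparison at .05. With no early claim of benefit possible, the interim reviews cannot raise the chance of a false claim of benefit, so .0451 is not needed.

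If the sponsor keeps the boundary, restate its power cost as about 1.6 to 3.1 points on the exact binomial basis, and require any estimate from an early stop to be labelled as exaggerated by selection.

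The cost is protocol wording. The one thing given up is the option to stop early for a very large culture benefit. That is a small loss for a pilot whose rule is already only a guideline.
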